3.1.1 Screening period

Patients with elective knee replacement, screened with informed consent to enroll patients, met all enrollment criteria and did not meet any of the exclusion criteria.

3.1.2 Treatment Period

Actively control blood pressure, blood pressure and blood sugar, correct anaemia and hypoproteinemia, and increase protein intake before surgery. The dietary plan was informed by the ward nurse: all patients were fasted with solid food 6 hours before surgery and took 200 milliliters of carbohydrates orally 2-3 hours before surgery.

The venous access was open after home invasion and was routinely monitored electrocardiogram(ECG), non-invasive blood pressure(NBP) , oxygen saturation(SpO₂), bispectral index (BIS). Parecoxib 40 milligrams of analgesia was given intravenously at 30 minutes before the start of the procedure. Adductor canal block (ACB) and Infiltration between popliteal artery and capsule of knee (IPACK) block were performed on the lower limbs of the surgical side using an ultrasound high-frequency line array probe before induction of the general anesthesia procedure.

Anesthesia induction: after static injection of Midazolam 0.03 milligrams / kilogram, Propofol 2 milligrams / kilogram , Sufentanil 0.4 milligrams / kilogram, Cisatracurium 0.2 milligrams / kilogram. The tracheal tube was inserted after 3minutes and mechanical controlled ventilation was performed mechanical controlled ventilation, fraction of inspired oxygen (FiO₂) 40%, oxygen flow 2 litres/ minutes, minute ventilation 7 milliliters / kilogram, respiratory rate (RR) 12 times/ inspiration-to-expiratory ratio(I: E)1:2, maintain partial pressure of carbon dioxide in endexpiratory gas (PETCO₂) 35-40 millimeters of mercury (mmHg) . Anesthesia maintenance: intravenous propofol 4~7 milligrams / kilogram/ hour, remifentanil 0.3-0.5 microgrammes/kilogram/ hour, maintain BIS 40~60. A restrictive fluid management strategy was adopted, with 6ml/ kg·h supplemented with physiological needs, blood loss was supplemented with hydroxyethylstarch fluid, and concentrated red blood cells were infused at hemoglobin (Hb) <80 grams / litre to maintain patient blood pressure and heart rate fluctuations less than ±20% of the basal value . Dexamethasone 5mg and totoxetron 2mg for prophylactic antiemesis were given intravenously at 30min before the end of the surgery. All patients used hydromorphone patient-controlled intravenous analgesia (PCIA) pump for continuous: 1ml / h, automatic control: 5ml, locking: 10min, limit: 35ml / h, adjust parameters according to the pain.

Internal postanesthesia care unit (PACU) management: Patients will randomly enter

the PACU into two study groups: early carbohydrate feeding group (EOF group) and conventional feeding group (control group). Routine feeding group (Group C): Patients in group C were observed with 60min of abnormal vital signs after extubation, and returned to the ward for fasting and fasting for at least 6 h, and began to eat gradually through the mouth after anal exhaust. Early carbohydrate feeding group (EOF group): The EOF group drank 10.5% of 5 ml/kg body weight (100ml containing 12.5g maltodextrin, fructose and glucose) after extubation in the resuscitation room. PACU management: Patients will randomly enter the PACU into two study groups: early carbohydrate feeding group (EOF group) and conventional feeding group (control group). Routine feeding group (Group C): Patients in group C were observed with 60min of abnormal vital signs after extubation, and returned to the ward for fasting and fasting for at least 6 h, and began to eat gradually through the mouth after anal exhaust. Early carbohydrate feeding group (EOF group): The EOF group drank 10.5% of 5 ml/kg body weight (100ml containing 12.5g maltodextrin, fructose and glucose) after extubation in the resuscitation room.

To evaluate the drinking criteria for patients in the EOF group: Steward wake score of 6 and wake level level 3, take 5 ml/kg body weight of 12.5% carbohydrate (100ml containing 12.5g maltodextrin, fructose, and glucose) according to the patient's consent. The process of drinking carbohydrates was to take 30ml orally first. After observing the swallowing without abnormality, the patient was ordered to drink the remaining drinks within 2h. After the patient returned to the ward, the liquid diet began to gradually overenter the normal diet. When the patient was able to tolerate the normal diet, v.

Evaluation process of the drinking index:

1. Steward score: Akefulness: 0-no response to stimulus; 1-some response to stimulus; 2-full awake.(2) Respiratory tract patency degree: 0 points-the patient's respiratory tract needs support; 1 points-the patient's respiratory tract can maintain patency without support; 2 points-the patient can cough according to the doctor's guidance.(3) Body activity degree: 1 points-the patient's limb has no activity; 2 points-the patient's limb has an unconscious activity; 3 points-the patient's limb can carry out conscious activities

2. Wakefulness classification according to the patient's consciousness performance: Level 0: the patient is completely asleep, Call without any response; Level 1: The patient is falling asleep, However, head and neck movement, eye opening or limb movement when breathing; level 2: the patient is awake, Have the same performance as level 1, At the same time can also open the mouth, stretch the tongue; Level 3: The patient is awake, Have the same performance as level 2, At the same time can also clearly say their own name, age and other information; Level 4: The patient is awake, Have the same performance as level 3, It can also accurately identify the surrounding environment, And tell you exactly where you are.

3. In addition to receiving different feeding treatment programs in the PACU, the two groups received the same care and diet program formulated by the same care group.

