1.2.2 Secondary study endpoints

1.2.2.1, Effectiveness study endpoint

- 1) The level of retinol-binding protein in venous blood on the day and 1d and 3d after surgery;
- 2) The insulin resistance index in venous blood was checked on the empty stomach on the morning, 1d and 3d after the operation;
- 3) NRS score of thirst and hunger at 2h, 6h and 8h after surgery;
- 4) Abating distension within 24h after surgery;
- 5) The incidence of hypoxemia and reflux aspiration within 24h after surgery;
- 6) Time of anal exhaust for the first time after surgery;
- 7) Time to leave bed for the first time after surgery;
- 8) Length of hospitalization;
- 9) Postoperative subject satisfaction score.

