3.1.3 The Follow-up Period

Record: Patients had fasting serum prealbumin, retinol-binding protein levels, and

insulin resistance index on the same day, 1 day and 3 days after surgery.

Record: 2 hours, 6 hours and 8 hours postoperative digital scores; bloating, hypoxemia and reflux aspiration occurred 24 hours after surgery.

Record: length of hospitalization, first anal exhaust time, first ambulation time, nausea and vomiting, and patient satisfaction.

4. Subject recruitment and protective measures

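### First flatus is an endpoint in both arms but a condition for eating only in the control arm, so the comparison of time to flatus is at risk of unequal ascertainment

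*Protocol*

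**What the plan says.** Protocol section 1.2.2.1, item 6, lists "Time of anal exhaust for the first time after surgery" among the effectiveness endpoints, without restricting it to one arm.

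Section 3.1.2 sets the feeding rules. Group C patients, after observation following extubation, "returned to the ward for fasting and fasting for at least 6 h", and then "began to eat gradually through the mouth after anal exhaust". For the EOF group the section says: "After the patient returned to the ward, the liquid diet began to gradually overenter the normal diet". No flatus condition is attached to that step.

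Section 3.1.3 names the items to be recorded, among them "first anal exhaust time, first ambulation time, nausea and vomiting, and patient satisfaction". It gives no method, assessor or interval of enquiry for flatus.

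Item 3 at the end of section 3.1.2 says that, apart from feeding in the PACU, "the two groups received the same care and diet program formulated by the same care group".

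**The concern.** In one arm the outcome event also opens the way to food; in the other arm nothing depends on it. Flatus leaves no objective trace, so its recorded time depends on somebody noticing it and saying so. In group C a hungry patient has a motive to mention it, and the nurse has to know about it before feeding can start. In the EOF arm neither motive exists. The protocol mentions no blinding, and the visible difference in feeding would make blinding on the ward difficult.

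The endpoint matters to the trial's argument, because the background section cites recovery of bowel motor function as a benefit of early oral intake. If recorded times in control are pulled earlier relative to EOF, a true benefit of early feeding could be hidden, or a delay could appear where none exists. Unequally collected event times cannot be restored at the analysis stage, so this is a matter of trial procedure and cannot be left to a statistical analysis plan.

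**Working it through.** **Step 1: the rules side by side**

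| | Group C | EOF group |
|---|---|---|
| Flatus time is an endpoint (1.2.2.1, item 6) | yes | yes |
| Minimum fast on the ward (3.1.2) | at least 6 h | none stated |
| Flatus needed before eating (3.1.2) | yes | no |
| Method of recording flatus (3.1.3) | not stated | not stated |

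The asymmetry is in the third row. Because of the second row, flatus before 6 h earns no food at that moment, so the incentive for prompt reporting operates from 6 h onward.

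**Step 2: direction**

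Observed difference (EOF minus control) = true difference + (mean recording delay in EOF − mean recording delay in control).

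The rule gives a reason for a shorter delay in control, so the second term is likely to be positive. Premature reports by hungry control patients would act in the same direction.

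**Step 3: size**

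The protocol states no figure for this endpoint, so there is nothing to reproduce. The following are assumptions.

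- EOF flatus is charted only at checks every k hours, and the event falls at random between checks: mean delay k/2.
- Control flatus is charted at once: mean delay 0.
- A fraction p of EOF patients, when asked, give the true time and that time is charted: mean EOF delay (1 − p) × k/2.

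| Shift in hours | k = 2 | k = 4 | k = 8 |
|---|---|---|---|
| No recall (p = 0): k/2 | 1 | 2 | 4 |
| Half recall accurately (p = 0.5): 0.5 × k/2 | 0.5 | 1 | 2 |
| All recall accurately (p = 1) | 0 | 0 | 0 |
| Both arms charted at the same checks: k/2 − k/2 | 0 | 0 | 0 |

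**Step 4: the 6 h fast**

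A simulation took identical true flatus times in both arms (lognormal, log-SD 0.5, 50 per arm, 3,000 runs; all assumed). EOF flatus was charted at the next check. Control flatus was charted at once from 6 h; before 6 h it was charted at 6 h or the next check, whichever came first. The 6 h were counted from the same origin as the flatus time.

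| Assumed median flatus time | Share of events before 6 h | Shift, k = 2 | k = 4 | k = 8 | Prompt in both arms |
|---|---|---|---|---|---|
| 6 h | 50% | 0.61 h | 1.37 h | 3.25 h | −0.01 h |
| 12 h | 8% | 0.95 h | 1.97 h | 3.92 h | 0.02 h |
| 20 h | 1% | 0.95 h | 1.98 h | 3.95 h | −0.01 h |

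The minimum fast reduces the shift only where many events fall before 6 h. Otherwise the result stays close to k/2, and with equally prompt recording it is about zero.

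**The case against.** The strongest reply is that the protocol does not show unequal recording. It says only that the time is recorded. Nurses may put the same question to everyone on the same rounds, and EOF patients may give the true time when asked. The k/2 figure follows directly from assuming no delay in one arm and rounding up in the other. This stands: a reader might infer that the comparison is biased, that flatus is self-reported, or that control patients report it at once, but the protocol states none of these. For the same reason no false-positive rate is offered. Such a rate would restate the assumed delay and would also need a sample size and a spread that the protocol does not give for this endpoint.

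It can also be said that the frequency of ward enquiry is an ordinary case-report-form detail. That would be enough if flatus were only an outcome. Here the protocol itself gives the arms unequal reason to report it, and sets no matching procedure, although it does fix clock times for thirst and hunger (2, 6 and 8 h).

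The likely shift works against EOF, so this mechanism would not manufacture an EOF benefit. That is correct and limits the consequence.

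Finally, the sentence on a common care and diet program might be read as evidence of different nursing attention. It is not; if anything it points towards equal care. Its conflict with the arm-specific ward diets is a separate inconsistency.

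**Conclusion.** The point holds as a risk, not as a demonstrated bias. The feeding rules in section 3.1.2 give control patients and staff a reason, from 6 h onward, to report promptly an outcome that is compared between arms, and section 3.1.3 sets no common way of recording it. The likely effect is earlier recorded times in control.

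Its size is unknown. It ranges from about zero, with like recording or accurate recall, to about k/2 hours if control is charted at once and EOF only at checks every k hours (1 to 4 h for assumed k of 2 to 8). Only a secondary endpoint is concerned; prealbumin is a blood measurement that this reporting mechanism does not touch. The change is worth making because it is cheap and because the data cannot be repaired afterwards.

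Separately, item 3 of section 3.1.2 and the ward diets described earlier in that section contradict each other and must be reconciled.

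**What to change.** Add to section 3.1.3 that ward nurses ask every patient in both arms about flatus at the same fixed clock times until first flatus. Define the endpoint time in both arms as the first positive scheduled check, with an interval-censored analysis as a sensitivity analysis. A spontaneous report between checks may still serve the feeding rule, which is unchanged, but does not set the endpoint time.

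The cost is one line of procedure and a short checklist on the nursing chart. Timing becomes slightly coarser in both arms. Premature yes answers from hungry control patients are not fully removed, since food still depends on the answer, and the report should say so.

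Reconcile the statement of a common diet program with the arm-specific ward diets in section 3.1.2, so that it is clear which parts of ward care are meant to be the same.

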4.2 Exclusion criteria

- Preoperative gastric emptying disorders, such as gastroesophageal reflux or previous surgery;
- Diabetes mellitus, severe renal insufficiency, or other severe metabolic diseases;
- History of motion sickness;
- Mental disorders, alcoholism, or a history of substance abuse;
- Patients with abnormal swallowing function;
- Maltodextrin, fructose allergy or intolerance;
- Surgery time was greater than 3 hours.

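### Patients are allocated at about PACU entry, before a wake-score and willingness check written for the EOF group only; this may cost power, and it opens the way to one-sided withdrawal under section 4.3

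*Protocol*

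**What the plan says.** **Allocation.** Protocol section 3.1.2 says, in a paragraph printed twice: "PACU management: Patients will randomly enter the PACU into two study groups". The wording is rough, but it places allocation at about PACU entry.

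**EOF group.** The drink is taken "after extubation in the resuscitation room", subject to conditions introduced for this group alone: "To evaluate the drinking criteria for patients in the EOF group: Steward wake score of 6 and wake level level 3". It is taken "according to the patient's consent", which is separate from the trial consent obtained at screening. A first 30 ml is followed by a swallowing check: "After observing the swallowing without abnormality, the patient was ordered to drink the remaining drinks within 2h".

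**Control group.** "Patients in group C were observed with 60min of abnormal vital signs after extubation", followed by return to the ward and at least 6 h of fasting. No wake score, willingness check or swallowing check is named.

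**Eligibility.** Section 3.1.1 describes screened patients who "met all enrollment criteria and did not meet any of the exclusion criteria". One exclusion in section 4.2, "Surgery time was greater than 3 hours", cannot be known at screening.

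**Withdrawal.** Section 4.3 lets the investigator take out subjects who do not complete the trial as the protocol specifies. It does not say whether they remain in follow-up.

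**Not stated.** The protocol does not say what happens to an EOF patient who does not meet the check or declines. It sets no time limit for meeting the check and gives no expected share of such patients.

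**The concern.** The main objective in section 1.1.1 is the effect of early oral carbohydrate on nutritional status, measured by prealbumin (section 1.2.1). A patient can be randomised to the drink and only afterwards be found not ready, or not willing, to take it. Because the check is not made in controls, the control patients who would also have failed it cannot be picked out later by any analysis.

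There are two ways to handle EOF non-starters, and each has a cost:

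- **Keep them as allocated.** The comparison is protected by randomisation, but the observed difference may shrink toward zero.
- **Withdraw them under section 4.3.** Only EOF patients can fail a check that only EOF patients face. EOF would then consist of patients who woke well and agreed to drink, while control would remain unselected.

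When to allocate, and what to record in controls, are protocol decisions. An analysis plan cannot recover a readiness assessment that was never made.

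**Working it through.** The protocol shown gives no sample size, effect size, SD, power or non-start rate, so there is no planned figure to reproduce. The calculations below illustrate size under stated assumptions.

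**Assumptions.** p is the share of EOF patients who never start and gain nothing: 5%, 10% or 20%. For power, I take a true difference of 0.5 SD, two-sided alpha 0.05 and 63 per arm, which gives 80% power when p = 0.

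**Step 1: dilution if all are analysed as allocated.** Observed effect = (1 − p) × true effect, that is 0.95, 0.90 or 0.80 of it. Power = Φ(0.5 × (1 − p) × √(63/2) − 1.96), ignoring the negligible opposite tail. The first term is 2.666, 2.526 or 2.245, so power is 76.0%, 71.4% or 61.2%.

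**Step 2: fair comparison with allocating after the check.** Let N be the number of consented patients.

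- Current timing: N patients at a diluted effect give an effective sample of N(1 − p)².
- Allocation after the check: N(1 − p) patients at full effect give N(1 − p).
- Ratio: (1 − p)² / (1 − p) = 1 − p.

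The loss due to timing is therefore p.

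| p | Current timing, (1 − p)² | After the check, 1 − p | Relative loss |
|---|---|---|---|
| 5% | 0.9025 | 0.95 | 5% |
| 10% | 0.81 | 0.90 | 10% |
| 20% | 0.64 | 0.80 | 20% |

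In terms of power, allocation after the check leaves 59.85, 56.7 or 50.4 per arm on average. Φ(0.5 × √(n/2) − 1.96) then gives 78.1%, 75.9% or 70.9%, against 76.0%, 71.4% or 61.2% under the current timing.

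**Step 3: bias if EOF non-starters are withdrawn.** Let g be the outcome gap, in SD, between patients who would and would not start, and suppose the drink has no effect. Removing the non-starters from EOF alone shifts the EOF mean by p × g. The standard error is √(1/63 + 1/(63(1 − p))), which is 0.1805, 0.1831 or 0.1890.

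| p | g (SD) | Bias (SD) | Two-sided type I error |
|---|---|---|---|
| 5% | 0.5 | 0.025 | 5.2% |
| 10% | 0.5 | 0.05 | 5.9% |
| 20% | 0.5 | 0.10 | 8.3% |
| 5% | 1.0 | 0.05 | 5.9% |
| 10% | 1.0 | 0.10 | 8.5% |
| 20% | 1.0 | 0.20 | 18.5% |

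The values of g are also assumptions.

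**Step 4: the check as printed.** The three Steward items in section 3.1.2 score 0–2, 0–2 and 1–3, so the total runs from 0 + 0 + 1 = 1 to 2 + 2 + 3 = 7. The required score of 6 is therefore not the maximum of the scale as printed. The text also does not say whether 6 and level 3 are exact values or minimums. These passages must be reconciled before the check can be applied to anyone.

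**The case against.** The strongest reply is that comparing two feeding strategies in everyone who reaches the PACU is a legitimate question. Patients who would fail the check are balanced between arms by randomisation, and the analysis set may be fixed in a statistical analysis plan that is not shown. This stands: analysed as allocated, the comparison is unbiased, and the missing check in controls does no harm by itself.

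Several stronger readings are tempting, but the protocol does not support them:

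- **Dilution is certain.** No non-start rate is given. With no deadline for the check, a slow waker may drink late rather than never. A patient who fails the swallowing step has already had 30 ml. Section 4.2 already excludes abnormal swallowing. The ward liquid diet for EOF is not expressly tied to having had the drink, although item 3 of the same section says that diet outside the PACU was the same in both arms; these statements must be reconciled. Hence (1 − p) is an upper bound on dilution.
- **The loss is 10%, 19% or 36%.** That is 1 − (1 − p)² and ignores that allocating after the check also loses these patients.
- **Allocation precedes extubation.** This is the likely order but is not stated, and the point does not need it.
- **The arms share no time zero.** Sections 1.2 and 3.1.3 time prealbumin and the thirst and hunger scores from surgery in both arms.
- **The 3-hour exclusion is unknown at allocation.** Surgery has ended by PACU entry, so operating time is available. What is missing is a stated instruction to confirm it.

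**Conclusion.** The point holds as a design weakness worth correcting. The protocol allocates at about PACU entry, ahead of a readiness and willingness check that only EOF patients face, and section 4.3 permits withdrawals that, for this check, could fall on EOF alone.

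For an as-allocated analysis the harm is lost power only. It is small at 5% non-starters and material at 20%, and its true size cannot be found from the protocol. For an analysis that drops EOF non-starters the harm is bias, ranging from negligible to serious depending on how many there are and how far their outcomes differ. The protocol does not say that they will be dropped; section 4.3 only allows it. A reader should not conclude that the planned comparison is biased as it stands.

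**What to change.** In section 3.1.2:

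- Assess the awakening criteria, once reconciled, and willingness to drink identically in all patients.
- Confirm the operating-time exclusion at the same point, and open the allocation only then.
- Keep endpoint times counted from surgery, as in sections 1.2 and 3.1.3.
- Leave the 30 ml swallowing step in EOF as part of the treatment. It stays after allocation, so the change removes most, but not all, of the ways a randomised patient can fail to take the drink.

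In section 4.3, state that every randomised patient remains in follow-up and in the primary analysis whether or not the drink is completed, subject to the patient's right to withdraw consent.

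**Cost.** Protocol wording, a somewhat later opening of the allocation in the PACU, and wake scores recorded in controls too. Patients who do not reach the check or are unwilling are not randomised, so results apply to those who reach it and are willing to drink, and some consented patients are lost to recruitment.

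### The limb item of the Steward score is numbered 1 to 3 while the other two items run 0 to 2, so the drinking threshold of 6 is one point short of full recovery

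*Protocol*

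**What the plan says.** Section 3.1.2 (Treatment Period) sets the condition for drinking in the early-feeding group: a "Steward wake score of 6 and wake level level 3". Item 1 of the evaluation process in that section then defines the Steward score item by item.

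- **Wakefulness:** 0, 1 or 2, from no response up to fully awake.
- **Airway:** 0 if support is needed, then "1 points-the patient's respiratory tract can maintain patency without support", then "2 points-the patient can cough according to the doctor's guidance".
- **Limb activity:** it starts at "Body activity degree: 1 points-the patient's limb has no activity", gives 2 for unconscious movement, and ends at "3 points-the patient's limb can carry out conscious activities".

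No total range is given. The text does not say whether 6 means exactly 6, at least 6, or the full score.

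Two other checks surround the score. Wake level 3 is cumulative: it includes level 2 ("At the same time can also open the mouth, stretch the tongue") and adds "At the same time can also clearly say their own name, age and other information". The drink itself is staged, with 30 ml first: "After observing the swallowing without abnormality, the patient was ordered to drink the remaining drinks within 2h".

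**The concern.** Two items start at 0 and the third starts at 1. A threshold of 6 would be the maximum of three items scored 0 to 2, but it is not the maximum of the scale as printed. The gate then asks for less than full recovery, and the point that can be missing may be cough on instruction.

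The gate governs when patients aged 65 or over (section 4.1) take 5 ml/kg by mouth soon after general anaesthesia. Reflux aspiration and hypoxaemia within 24 hours are a listed secondary endpoint (section 1.2.2.1, item 5). A rule that decides when the study drink may be given should have one meaning at the bedside, and that meaning should include the airway sign the scale was built to capture.

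**Working it through.** **Inputs**, all from section 3.1.2: wakefulness W in {0, 1, 2}; airway A in {0, 1, 2}; limb activity L in {1, 2, 3}; threshold 6. The protocol states no scale total, so there is no figure of its own to reproduce.

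**Range of the printed scale.** Total = W + A + L.

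- Minimum: 0 + 0 + 1 = 1.
- Maximum: 2 + 2 + 3 = 7.

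The threshold of 6 is one point below the maximum.

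**Which profiles pass.** There are 3 × 3 × 3 = 27 profiles (W, A, L).

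| Profile | Total | What is missing |
|---|---|---|
| (1,2,3) | 6 | responds to stimulus but not fully awake |
| (2,1,3) | 6 | airway open, no cough on instruction |
| (2,2,2) | 6 | limb movement only unconscious |
| (2,2,3) | 7 | nothing |

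- Exactly 6: the first three profiles pass and the fully recovered patient does not.
- 6 or more: all four pass, and one of the four is full recovery.

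**Adding wake level 3.** A patient who is awake and states name and age can be taken to have W = 2, which removes (1,2,3). If conscious limb movement is also assumed (L = 3), the airway item alone decides the total:

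| Airway finding | Printed scale (L = 3) | Limb rescored 0 to 2 (L = 2) |
|---|---|---|
| Needs support (A = 0) | 2 + 0 + 3 = 5 | 2 + 0 + 2 = 4 |
| Open, no cough on instruction (A = 1) | 2 + 1 + 3 = 6 | 2 + 1 + 2 = 5 |
| Coughs on instruction (A = 2) | 2 + 2 + 3 = 7 | 2 + 2 + 2 = 6 |

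On the printed scale, exactly 6 admits only the patient who does not cough on instruction, and 6 or more admits that patient together with the one who does. With limb activity rescored 0 to 2, the total runs from 0 to 6, a score of 6 is reached only by (2,2,2), and the patient who does not cough is held back at 5.

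Without the assumption on limb movement, printed (2,2,2) also stays admitted. The profile (2,1,3) passes either way.

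**Whether another check covers cough.** Wake level 3 tests mouth opening, tongue movement and speech. The 30 ml step tests swallowing. Neither asks for a cough, which appears only as airway score 2.

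**The case against.** The strongest reply is that this is a copying or translation slip in a named, existing scale. The surrounding text has other slips of wording. Section 6.2 requires protocol training for all researchers and systematic training on important scales, so staff may well score limb activity 0 to 2 and treat 6 as the full score. In that case nothing goes wrong. That is plausible, and it is why the consequence is conditional. It does not settle the matter, because the protocol prints its own scoring and that is the text staff are trained on and inspectors check against. Staff who follow it apply a weaker gate than staff who correct it silently.

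A second reply is that the exposed group may be very small. A patient who speaks clearly, puts out the tongue and moves purposefully will usually cough when asked. The first 30 ml is an observed swallow, which bears directly on safe drinking. Airway score 1 already means an open airway without support, and section 4.2 excludes abnormal swallowing and gastric-emptying disorders. All of this stands and limits the weight of the point.

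A third reply is that nobody would apply a recovery threshold as exactly 6 and turn away the fully recovered patient. That is fair, but the finding does not need that reading, since at least 6 still admits the patient who does not cough.

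Finally, wake level 3 does not strictly establish conscious limb movement, because section 3.1.2 lists limb movement only as one alternative response. This is correct, and it is why that step is labelled an assumption. Dropping it leaves more incomplete profiles admitted, not fewer.

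**Conclusion.** The point holds as a minor safety correction. As printed, the scale totals 1 to 7 and the threshold of 6 is one short of full recovery. Three profiles score exactly 6, none of them full recovery; four score 6 or more, one of them full recovery. These are counts of score profiles, not of patients.

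That 6 was meant as the full score is an inference from the 0 to 2 pattern of the other two items; the protocol does not say so. Any effect on patients depends on the scale being scored as printed, and how many would be awake and moving purposefully without coughing on instruction cannot be computed from the document. No effect on prealbumin, sample size or error rates is shown.

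**What to change.** Renumber the limb item in section 3.1.2 as 0 for no activity, 1 for unconscious activity and 2 for conscious activity, so that 6 is the full score and can be reached only with cough on instruction. Alternatively, keep 1 to 3 and raise the threshold to 7; only (2,2,3) then passes, which is the same fully recovered patient.

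The cost is three digits in the first case and one in the second. Sample size, visits, randomisation and endpoints are unchanged.
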